9.2.3 Secondary Efficacy Analyses

The ITT population will be used for the secondary analyses. As a secondary efficacy analysis, data will be analyzed at each post-baseline visit to evaluate the proportion of patients achieving a composite treatment success, defined as a response on both the IGA-C and SSA-C scales. The analysis models for the primary efficacy analysis will be used.

Treatment success based on the SSA alone will also be analyzed using the above definition and analysis models.

In addition, mean change from Baseline IGA will be analyzed using an analysis of variance (ANOVA) model. The first model contrasts will be separate evaluations of the effect of each active group vs. vehicle. Additional contrasts will be performed comparing pooled active treatment groups vs. vehicle and comparing the two active treatment groups. Contrasts will be made within the ANOVA model using LSMeans and the appropriate pooled error term, with no alpha adjustment for multiple comparisons. An analysis of covariance (ANCOVA) model with baseline average IGA score as the covariate will be used if it yields greater sensitivity than the ANOVA model.

A similar model will be used to analyze mean change from baseline SSA.

Primary and secondary analyses will also be performed based on IGA and SSA evaluations made at rest.

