3.2 Treatment Groups / Sample Size

The following dose groups and sample sizes are planned:

Dose Group		Vehicle	690 U	1,100 U	Σ Total
Cohort 1	N =	12	24		
Cohort 2	N =	12		24	
Total	N=	24	24	24	72

The treatment area will be preconditioned with a Dermaroller MC 905, 0.5 mm. ET-01 will be applied immediately after pre-conditioning.

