9.2.2 Primary Efficacy Analysis

The IGA and SSA scores (Crow’s Feet Wrinkle scale) are evaluations performed by the investigator and the subject, respectively, measured both at rest and on contraction. For analysis purposes they will be averaged between left and right sides prior to analysis. In the event one side has missing data for a visit, the result from the side with non-missing data will be used instead of an average value. These scores will be treated as continuous measures for calculating means and performing ANOVA analyses, and they will be used as described below to derive binary indicators of treatment success, which will be analyzed as dichotomous measures.

Efficacy analyses will be based on the assessments from the treatment areas, i.e. the lateral canthal area only. Alpha will be set at 0.05 using two-tailed tests. The Crow’s Feet Wrinkle scale is an ordinal categorical scale ranging from 0 to 4. As described above, left- and right-side values will be averaged, and the averaged values will be used for analysis.

The Investigator’s Global Assessment (IGA) is the primary efficacy parameter, and the evaluation of each active drug group vs. vehicle will be the primary comparisons. A comparison between the two active drug groups will also be performed, along with a

comparison between the two active drug groups pooled vs vehicle. Results will be summarized for each treatment group and at each visit using frequency distributions.

For the primary efficacy analysis, "IGA on contraction" (IGA-C) data will be analyzed at each visit to evaluate the proportion of patients achieving treatment success (responder). For this analysis, a response will be defined as a reduction from baseline in IGA-C by at least 2 points. A separate chi-square test will be used to evaluate the effect of each dose of ET-01 compared to Vehicle. A chi-square test will also be performed evaluating the overall effect of active drug vs vehicle by collapsing the two active drug treatment groups for this analysis. In addition, a separate chi-square test will be used to compare the two active drug groups. The ITT population will be used for this analysis.

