9.3 Significance

Unless otherwise specified, all statistical tests will be conducted against a two-sided alternative hypothesis, employing a significance level of 0.05.

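### The secondary mean-change model is left to an undefined sensitivity criterion that needs outcome data; baseline-adjusted ANCOVA should be named in advance

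*Combined protocol and SAP*

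**What the plan says.** Section 9.2.3 of the combined protocol and SAP states that "mean change from Baseline IGA will be analyzed using an analysis of variance (ANOVA) model". Four contrasts follow: each dose against vehicle, pooled active against vehicle, and dose against dose. They are made "with no alpha adjustment for multiple comparisons". The section then adds that an ANCOVA "model with baseline average IGA score as the covariate will be used if it yields greater sensitivity than the ANOVA model". For the subject's score, "A similar model will be used to analyze mean change from baseline SSA". The section closes by repeating the primary and secondary analyses on the at-rest scores.

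The error rate is set in two places. Section 9.2.2 says "Alpha will be set at 0.05 using two-tailed tests", and Section 9.3 says that, unless otherwise specified, "all statistical tests will be conducted against a two-sided alternative hypothesis, employing a significance level of 0.05".

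The plan does not define sensitivity. It does not say whether the choice is made once or separately by visit, scale, condition or contrast, nor whether it is made on blinded data. Section 9.5 promises a separate SAP before study completion and unblinding, but the documents contain no text that settles the model. Section 9.2.5 allows an efficacy interim analysis once all subjects have passed Week 4.

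**The concern.** Choosing between two tests on the outcome data they are meant to test can break the nominal level. If the analyst fits both models and keeps the one with the smaller p-value, the result is the minimum of two correlated p-values, and rejecting when it falls below 0.05 has a true error rate above 5%.

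The rule could also be applied many times. If the models are fitted at each of the seven post-baseline visits, there are 2 scales x 2 conditions x 7 visits = 28 fits with four contrasts each. The text would let the model differ from one fit to the next, which would make results hard to compare across visits.

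The baseline score is already collected on every subject, so making its use conditional gains nothing.

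**Working it through.** **Inputs from the documents.** Three arms of 24, 72 in total (Section 3.2); two-sided 0.05 (Sections 9.2.2 and 9.3); the four contrasts of Section 9.2.3; baseline IGA on contraction limited to 3 or 4, so the left-right average is 3, 3.5 or 4, and at-rest baseline limited to 1 to 3 (Section 5.1).

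**Assumed inputs.** Section 9.1.1 gives no effect size, SD or correlation. The correlation r between baseline and change is therefore ranged from 0 to 0.85 in absolute value. Errors are taken as normal, although averaged scores move in half-point steps. Baseline is either normal or the three discrete values.

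**Tests compared.** For a contrast c, with group means of change (ȳ) and of baseline (x̄), pooled within-group slope b and within-group baseline sum of squares Sxx:
- ANOVA: t = c'ȳ / √(MSE₀ · Σc²/24), 69 df.
- ANCOVA: t = (c'ȳ − b·c'x̄) / √(MSE₁ · [Σc²/24 + (c'x̄)²/Sxx]), 68 df.

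**Step 1: the plan's own level.** With 40,000 simulated null trials per setting (Monte Carlo SE 0.0011), ANOVA used alone rejects in 4.8% to 5.1% of trials and ANCOVA used alone in 4.9% to 5.2%. Either model, fixed in advance, delivers the stated 5%.

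**Step 2: three readings of the rule.** Type I error of one dose-vs-vehicle contrast:

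| Assumed abs(r) | (a) Smaller p-value |
|---|---|
| 0 | 5.4% |
| 0.2 | 5.8–6.0% |
| 0.3 | 6.4% |
| 0.5 | 7.3% |
| 0.7 | 8.0–8.3% |
| 0.85 | 8.8–8.9% |

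Over the same settings, reading (b), the smaller residual mean square, gives 4.9% to 5.2%. Reading (c), ANCOVA when the covariate has p < 0.05, gives 4.9% to 5.4%.

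**Step 3: a concrete on-contraction case.** Assume baseline SD 0.46, follow-up SD 0.70 and baseline/follow-up correlation ρ of 0.2 to 0.5. The SD of change is √(0.46² + 0.70² − 2ρ·0.46·0.70), and r = (ρ·0.70 − 0.46) / SD of change:
- ρ = 0.2: SD 0.757, r = −0.42
- ρ = 0.3: SD 0.713, r = −0.35
- ρ = 0.5: SD 0.616, r = −0.18

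Simulated under these inputs, the smaller-p reading gives 5.8% to 7.0% per contrast, in line with the table. The chance of at least one false-positive dose is 10.4% to 12.4%, against about 9% with ANCOVA fixed. At rest, where the baseline range is wider (assumed SD 0.71), the per-contrast figure is 7.3% to 8.0%.

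**Step 4: precision given up by ANOVA.** The ratio of residual variances, ANOVA to ANCOVA, is (0.46² + 0.70² − 2ρ·0.46·0.70) / (0.70²·(1 − ρ²)). For ρ = 0.2, 0.3 and 0.5 it is 0.5728/0.4704 = 1.22, 0.5084/0.4459 = 1.14 and 0.3796/0.3675 = 1.03.

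**Step 5: power with ANCOVA fixed.** For an assumed 0.8 SD effect of the high dose, ANCOVA against ANOVA:
- r = 0: 77.4% vs 78.0%
- abs(r) = 0.3: 81.3% vs 78.1%
- abs(r) = 0.5: 88.0% vs 78.1%
- abs(r) = 0.7: 96.8% vs 77.7%

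**The case against.** The strongest reply is that sensitivity, in an ANOVA setting, ordinarily means precision, and that the same paragraph speaks of the pooled error term. On that reading the selection does no measurable harm: the type I error stays at about 5%. This stands, and it rules out the flat statement that the rule inflates the false-positive rate. It does not rescue the clause. Under the Step 3 inputs ANCOVA has the smaller residual mean square in 69% to 99.7% of trials, so the conditional adds little, and the text still permits the harmful reading.

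A second reply is that Section 9.5 provides a SAP before unblinding, where the model can be fixed. That is the right place, but no text there does it, and a SAP that repeats the protocol sentence would keep the rule. The Week 4 interim analysis could also bring outcome data into view first.

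A reader might infer three stronger things that the documents do not support:
- **That the choice is made on unblinded data.** Section 9.2.3 gives no timing.
- **That confidence intervals would be too narrow.** Section 9 plans none for mean change.
- **That the trial's main conclusion is at risk.** The primary analysis is a set of chi-square tests on IGA-C responders (Section 9.2.2), which this rule does not touch.

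**Conclusion.** The point holds as a moderate one. The model for a family of secondary analyses is not fixed, and the criterion for choosing it is undefined and depends on outcome data, so the stated 5% level is not assured. The possible excess runs from almost nil (residual variance or covariate significance) to about 1 to 2 percentage points per contrast in the concrete on-contraction case, and nearly 4 points at the far end of the assumed correlation range (smaller p-value). The true correlation may be small on contraction, because baseline there is restricted to 3 to 4.

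Naming the model removes only the selection component. With a fixed model and four unadjusted contrasts, the chance of at least one false positive is still about 12% to 13% per visit and endpoint (13.6% to 21.7% under the smaller-p reading). Multiplicity across contrasts, visits and scales is a separate matter.

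**What to change.** Before unblinding, and before any Week 4 interim analysis, replace the conditional sentence in Section 9.2.3 with:

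> Change from baseline in IGA (and SSA) will be analysed at every visit by ANCOVA with treatment as factor and the corresponding baseline average score as covariate.

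Delete the greater-sensitivity clause, carry the same sentence into the SAP, and show ANOVA only as a labelled sensitivity analysis.

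The cost is one sentence, with no effect on subjects or data collection. The statistical downside is a power loss of about 0.6 points (77.4% against 78.0%, assumed 0.8 SD effect) if baseline is uncorrelated with change.

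Cohort should not be added as a factor as part of this change. Each dose is given in one cohort only, beside 12 vehicle subjects (Section 3.2), so a cohort term restricts each dose to comparison with its own 12. The dose-vs-vehicle variance goes from 1/24 + 1/24 = 0.0833σ² to 1/24 + 1/12 = 0.125σ², a rise of 50%. The dose-vs-dose variance goes from 0.0833σ² to 2 × 0.125 = 0.25σ², a threefold rise. For the same 0.8 SD effect, power for dose against vehicle would fall from 78% to about 61% before any gain from baseline. Whether to adjust for cohort is a separate decision with its own trade-off.

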9.2.4 Safety Analysis

The assessment of safety will be based mainly on the frequency of adverse events. Other safety data (e.g., vital signs and special tests) will be summarized as appropriate.

Adverse events will be coded using a current MedDRA dictionary and summarized by presenting, for each treatment group, the number and percentage of subjects having any adverse event, having an adverse event in each body system (System Organ Class), and having each coded individual adverse event. Other adverse event information collected (e.g., severity/intensity or relationship to study medication) will be listed as appropriate.

Data from other tests will be listed, notable values will be flagged, and any other information collected will be listed as appropriate. No inferential statistical tests are planned for safety data but may be performed on an ad-hoc basis to highlight any comparisons that may warrant further consideration.

9.2.5 Interim Analysis

Interim analyses for efficacy and safety may be conducted after all subjects have passed the Week 4 visit. As there is only one treatment at Baseline and, therefore, interim analyses will not alter the conduct of the trial, no alpha adjustment will be required.

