5.4.1 Subject Unblinding Procedures

Randomization lists will be maintained by the sponsor. In case of serious adverse events or other medical emergencies that make it necessary to unblind the treatment code for a specific subject, the investigator will, after consultation with the sponsor, submit a written request for unblinding to the Medical Monitor. The request will be documented, and the applicable information will be sent to the investigator via fax or e-mail. Unblinded subjects will be discontinued from the study.

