7.3 Stopping Rules

The study is designed as a sequential, overlapping cohort, dose-escalation trial. Enrollment will be halted after each cohort until a safety review has been completed.

- Enrollment will be halted in the event that one serious adverse event (SAE), considered to be probably or definitely related to the administration of study medication, is observed.
- Enrollment will be halted in the event that one AE is observed considered to be indicative of distant spread of study medication or unintended exposure to other beings.
- The Sponsor may stop the study in its entirety or discontinue individual study centers at its discretion for any reason or, e.g. if it is observed that the protocol or sound clinical practices are not being followed, or for any other reasons.

The study protocol calls for only one single application of study medication at Baseline (Week 0). Since there is no continuous treatment, no stopping rules for subjects are

applicable and subjects will be encouraged to participate in the study until the scheduled termination visit at Week 26.

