9.5 Deviation Reporting

A Statistical Analysis Plan will be created prior to the completion of the study and unblinding of the database. Any deviations from or additions to the statistical analyses specified in the protocol will be described and justified in the Statistical Analysis Plan.

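### Section 9.5 does not say that the SAP must be final before the Week 4 efficacy interim, and 9.2.5 sets no limit on who sees its results by arm

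*Combined protocol and SAP*

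**What the plan says.** - **Interim (9.2.5).** "Interim analyses for efficacy and safety may be conducted after all subjects have passed the Week 4 visit". The reason given for no safeguard is that "interim analyses will not alter the conduct of the trial, no alpha adjustment will be required". The section does not say who runs the analysis or who receives it.
- **SAP timing and role (9.5).** "A Statistical Analysis Plan will be created prior to the completion of the study and unblinding of the database". Also: "Any deviations from or additions to the statistical analyses specified in the protocol will be described and justified in the Statistical Analysis Plan". The interim is not mentioned.
- **Primary analysis (9.2.2).** The endpoint is a reduction of at least 2 points in IGA-C, compared by chi-square test. "Alpha will be set at 0.05 using two-tailed tests", and "the evaluation of each active drug group vs. vehicle will be the primary comparisons". The test is repeated at each visit and no visit is named as primary. Pooled-active and dose-versus-dose tests are added.
- **Secondary model (9.2.3).** Mean change is analysed by ANOVA, or by ANCOVA if that proves more sensitive.
- **Blinding (3.6, 5.4.1).** Subjects and investigators are kept unaware of allocation; the sponsor is not mentioned. "Randomization lists will be maintained by the sponsor".
- **Schedule (3.3, 3.5, 7.2).** IGA and SSA are recorded at every visit. Weeks 8, 12, 18 and 26 follow Week 4.

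**The concern.** Two matters are left open together.

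The first is the order of the SAP and the interim. The SAP is the only remaining document that can settle the visit and the model, and it may alter the protocol analyses. If it is written after someone has seen response by dose at Weeks 1, 2 and 4, those choices can follow the results, and the nominal 5% level no longer describes the claim.

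The second is the later ratings. IGA and SSA are subjective grades. Blinding to individual allocation does not cover knowledge of group results. Under 4.2, dose level follows order of enrolment, and under 3.2 each cohort is 24 active to 12 vehicle. A rater who learned how one dose had performed could therefore form an expectation for a whole cohort without any code being broken.

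The reason in 9.2.5, that conduct will not change, answers neither matter.

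**Working it through.** The plan gives no power, effect size or response rate (9.1.1 refers only to interim results of two other studies), so there is no stated figure to reproduce. Steps 1 to 4 compare the sections; step 5 sizes the consequence.

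**1. Timing.** The earliest interim is the last subject's Week 4 visit. That subject then has 26 − 4 = 22 weeks and four rating visits left.

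**2. Are treatment codes needed?** 9.2.5 does not use the word unblinded, and the analysis is optional. But a remark on alpha adjustment has meaning only if treatments are tested against each other, and that needs the codes, which the sponsor holds.

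**3. Does 9.5 place the SAP first?** There are two readings.
- Strict: any use of the codes unblinds the database, so the SAP precedes the interim.
- Final unblinding only: 9.5 couples unblinding with study completion, and section 8 likewise speaks of unblinding as the step before adverse events are analysed for the clinical study report. On this reading the SAP may follow the interim.

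The text does not choose between them.

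**4. What is still open for the SAP?** The primary visit (seven post-baseline visits), ANOVA or ANCOVA, whether a per-protocol analysis is done (9.1.2), and any addition or deviation.

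**5. Size under no drug effect.**

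From the documents: 24 per group with a shared vehicle group; two-sided 0.05; two primary comparisons; three visits up to the interim, hence 2 × 3 = 6 tests. Assumed: the same response rate p in all groups, and a latent between-visit correlation ρ of 0.5 to 0.8.

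Model: for each subject and visit, Z = √ρ·S + √(1−ρ)·E, with S fixed for the subject and E new at each visit. The subject responds if Z exceeds the standard normal quantile at 1 − p. Test: Pearson chi-square without continuity correction, at least 20,000 simulated trials per scenario.

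Reference values if the tests were independent: two tests, 1 − 0.95² = 0.0975; six tests, 1 − 0.95⁶ = 0.265. The shared vehicle group and repeated measurement bring the simulated values somewhat below these.

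| Assumed response rate | Expected responders per group | At least one of six tests p < 0.05 |
|---|---|---|
| 10–30% | 2.4–7.2 | about 21–26% |
| 8% | 1.9 | 17–19% |
| 5% | 1.2 | about 9% |
| 3% | 0.7 | 2–3% |
| 2% | 0.5 | under 1% |

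Comparators at 10–30%: both doses at one fixed visit, about 8–10%; one dose at one fixed visit, about 5%. The fair comparator is 8–10%, since the protocol has two primary dose comparisons. Against it, the six-test figure is about 2.6 times as large (21/8 and 26/10). At low response rates the chi-square test is conservative with so few responders, and the fixed-visit figure falls too.

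**Model choice.** Taking the smaller p-value of ANOVA and ANCOVA for one contrast rejects in about 6.8–7.8% of null trials instead of 5% (24 per group, assumed baseline-to-post correlation 0.3 to 0.7).

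**The case against.** **SAP order.** A reader might infer that the protocol plans to write the SAP after an unblinded look. It does not. 9.5 requires the SAP before database unblinding, and the strict reading puts it before any comparison by arm. This objection stands: what remains is an ambiguity, not a stated sequence.

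**Conflict with 7.3.** A reader might also set 9.2.5 against "The Sponsor may stop the study in its entirety or discontinue individual study centers at its discretion for any reason". The documents do not support a conflict. That is a general reserved right. 9.2.5 says that the interim will not alter conduct, and 9.4 says that no interim analysis outside the stopping rules is planned that could end the trial. By the interim date, enrolment and the single application are complete for everyone.

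**Rater bias.** Both groups of raters are blinded to allocation, and 5.4.1 limits code release to serious adverse events and other emergencies, on written request. Nothing provides for group results to reach the sites. So this is an unprotected route, not a planned event. It remains true that nothing restricts who receives group results.

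**Magnitude.** The inflation is multiplicity from two doses and an unnamed visit. It exists with or without an interim, and signing the SAP early while every visit still counts would leave it unchanged. This also stands, and it is why the fix must include a primary visit.

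**Room for choice.** 9.2.2 already fixes the endpoint, responder cut-off, test, population and comparisons, and SAP changes must be justified. That narrows the freedom for the primary analysis mainly to the visit and the dose emphasised.

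**Conclusion.** The point holds as a gap that should be closed at low cost. The protocol permits an efficacy comparison by arm while subjective ratings still have up to 22 weeks to run. It does not say whether the SAP must come first, and it does not restrict who receives the results.

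If visit and dose were chosen from the Week 1 to 4 results, the chance of a false positive would be about 21–26% at an assumed 10–30% response rate, against 8–10% with both doses at one fixed visit. The figure depends heavily on that assumption: it is about 9% at a 5% response rate and 2–3% at 3%, and the documents give no rate. It measures the open choice of visit and dose. The interim's contribution is to let that choice be made with results in view. Possible bias in later ratings cannot be sized from the documents and depends on group results reaching raters.

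**What to change.** - **9.5:** require the SAP to be final and signed before any comparison by treatment, and state that unblinding includes the interim. The SAP should name one primary visit for the IGA-C responder analysis and fix either ANOVA or ANCOVA for mean change.
- **9.2.5:** state who runs the interim (preferably a statistician without site contact) and who receives it. State that group-level and subject-level results are withheld from investigators, subjects and site-facing sponsor staff until the Week 26 lock.

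Early sign-off without a primary visit would not reduce the error rate. With one visit fixed, the two unadjusted dose comparisons still carry about 8–10% at response rates of 10–30%.

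Cost: protocol wording, an earlier SAP sign-off, and fewer sponsor staff seeing interim efficacy results before lock. No subjects or visits are added.
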